6.3.3 Reporting to Hospital Risk Management

Participating investigators will report to their local Risk Management office any subject safety reports or sentinel events that require reporting according to institutional policy.

7. OTHER THERAPIES

If systemic anti-cancer treatment is urgently required during the two weeks of study treatment, the subject will be removed from the study and replaced. However, patients will be allowed to receive concurrent immunotherapy.

During the Phase I portion, if clinically indicated, systemic therapy can be given and the subject will remain evaluable for the phase I (toxicity) portion. Surgery (other than to index lesions) will be allowed. These patients will be scored as unevaluable for response assessment.

During the Phase II portion, if systemic therapy is needed prior to the 6 week post-treatment assessment time, that subject but will be scored as UNEVALUABLE for response assessment but will be followed for toxicity. Surgery (other than to index lesions) is allowed if clinically indicated and the subject will remain evaluable.

However, if the reason for non-protocol surgery or chemotherapy is disease worsening of the index lesions, those patients would be scored as disease progression

Patients may receive Decadron orally prior to each fraction of radiotherapy per physician discretion.

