6.2 Dose-limiting toxicities (DLTs)

DLTs are toxicities experienced between the start of the stereotactic radiotherapy and 6 months after radiotherapy. DLTs will be graded according to the CTEP active version of the National Cancer Institute's (NCI) Common Terminology Criteria for Adverse Events (CTCAE), located at:

http://ctep.cancer.gov/protocolDevelopment/electronic applications/ctc.htm.

The current version is CTCAE v4.0.

For this study, DLTs are defined as follows: The following grade 2 or higher toxicities:

- Myelitis
- Esophageal fistula, perforation, hemorrhage

The following grade 3 or higher toxicities considered to be a direct result of therapy:

- Pneumonitis
- Pericarditis, pericardial effusion
- Esophageal necrosis, stenosis, ulcer
- Dyspnea

The following grade 4 toxicities:

- Esophagitis
- Pericardial tamponade
- Pulmonary toxicity excluding infectious pneumonia
- Skin toxicity
- Hemoptysis/pulmonary hemorrhage

All grade 5 toxicities, including:

- Pulmonary toxicity including pneumonitis
- Excluding infectious pneumonia

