6.3 Toxicities and Adverse Events

6.3.1 Toxicities

6.3.1.1 All patients will be seen weekly by their treating radiation oncologist or coinvestigators (pediatric oncologist) while undergoing therapy. The following toxicities are expected and listed according to their likelihood and whether they are immediate or long term.

Evaluation of toxicity. All participants will be evaluable for toxicity from the time of their first treatment. Evaluation will be by the radiation oncology physician or by the patient's pediatric oncologist by physical examination and testing as indicated in the study calendar. Patients will be seen by the radiation oncologist for each treatment to assess toxicities and adverse events.

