11.4 Analysis of Secondary Endpoints

Secondary endpoints include relapse elsewhere in the lung and toxicities, and these analyses will be performed by dose level. The method of Kaplan and Meier will be used to characterize time to relapse elsewhere in the lung. All patients who receive any part of the treatment will be monitored for toxicity, and the percent of patients with various toxicities will be tabulated for each dose level. Assuming a total of 15 patients treated at a dose level, if the true probability of a rare toxicity is 5%, the probability of observing 1 or more rare toxicities is 54%. A 90% confidence interval for any toxicity will be no wider than 46%.

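### Section 7 gives opposite rules for a Phase I patient who urgently needs systemic therapy during SBRT, and no section says whether that patient's DLT still counts in the 3+3 decision

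*Combined protocol and SAP*

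**What the plan says.** Section 7 opens with a removal rule: "If systemic anti-cancer treatment is urgently required during the two weeks of study treatment, the subject will be removed from the study and replaced". One exception follows: "However, patients will be allowed to receive concurrent immunotherapy". The rule is not limited to Phase II, to patients who have not yet had a fraction, or to the response endpoint.

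The next paragraph of section 7 reads: "During the Phase I portion, if clinically indicated, systemic therapy can be given and the subject will remain evaluable for the phase I (toxicity) portion". It gives no time window. For Phase II, a patient needing systemic therapy before the 6-week assessment is "scored as UNEVALUABLE for response assessment but will be followed for toxicity".

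Two other sections define who is assessed for toxicity:

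- Section 6.3.1.1: "All participants will be evaluable for toxicity from the time of their first treatment".
- Section 11.4, on secondary endpoints: "All patients who receive any part of the treatment will be monitored for toxicity".

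Section 6.2 sets the DLT window: "DLTs are toxicities experienced between the start of the stereotactic radiotherapy and 6 months after radiotherapy". The two treatment weeks therefore lie inside it. Section 11.1 gives the decision rule: a dose level enters Phase II if none of three patients, or at most one of six, has a DLT. It does not mention patients who are removed or replaced.

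**The concern.** Take a Phase I patient who has received one or more fractions and then urgently needs chemotherapy in week 1 or 2. The first paragraph of section 7 takes the patient out of the study and fills the place. The second keeps the patient evaluable for toxicity. Both apply, with opposite results.

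What is at stake is the count of three or six that decides Phase II entry. If the patient has had a DLT, or has one later in the 6-month window, the documents do not say whether it enters that count or whether the replacement's outcome stands instead. They also do not say whether DLT follow-up continues after removal. Two people applying the plan in good faith could reach different decisions about the same dose level from the same data.

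**Working it through.** **1. The plan's own table.** Let p be the true DLT rate. If every treated patient counts,

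P(enter) = (1−p)³ + 3p(1−p)² × (1−p)³.

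| True DLT rate | 5% | 10% | 15% | 20% | 30% | 40% |
|---|---|---|---|---|---|---|
| Section 11.1 | 0.97 | 0.91 | 0.81 | 0.71 | 0.49 | 0.31 |
| Recomputed | 0.973 | 0.906 | 0.814 | 0.709 | 0.494 | 0.309 |

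The table is correct, on the basis that nobody who has a DLT is swapped out.

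**2. One replaced patient.** These figures need no assumption about how often removal happens. Take p = 0.30.

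*The removed patient has the only DLT in the first three.*
- Counted: three more patients must all be DLT-free, 0.7³ = 0.343.
- Replaced and not counted: the replacement is DLT-free (0.7), or has a DLT and the next three are clear (0.3 × 0.343). The sum is 0.7 + 0.103 = 0.803.

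*The removed patient has one of two DLTs in the first three.*
- Counted: 0, because the level has failed.
- Replaced and not counted: the replacement must be DLT-free and so must the next three, 0.7 × 0.343 = 0.240.

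**3. Average effect on the table.** Let d be the share of DLT patients, and n the share of DLT-free patients, who are removed, replaced and not counted. The DLT rate among counted patients is

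p′ = p(1−d) / [p(1−d) + (1−p)(1−n)],

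and p′ goes into the formula of step 1. The documents give neither d nor n, so the values below are assumptions. At p = 0.30:

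| d | n | p′ | P(enter) | Change from 0.494 |
|---|---|---|---|---|
| 10% | 0 | 0.278 | 0.539 | +0.045 |
| 25% | 0 | 0.243 | 0.614 | +0.120 |
| 20% | 5% | 0.265 | 0.567 | +0.073 |
| 10% | 10% | 0.300 | 0.494 | 0 |
| 5% | 20% | 0.337 | 0.420 | −0.074 |

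The sign depends on whether DLT patients or DLT-free patients are removed more often.

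**4. Does another section settle it?** Section 6.3.1.1 says when toxicity evaluation begins. Section 11.4 governs tabulation of toxicities, and section 6.3.2.3.2 governs reporting of serious events for 6 months after the last dose. All three keep events on record. None says who makes up the three or six patients in 11.1.

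**5. Counting every patient with at least one fraction as a full slot.** This would also shift the decision. Suppose one of the first three was only partly treated. At p = 0.30:

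- DLT risk zero in that patient: no DLT in the other two, 0.7² = 0.49; exactly one, 2 × 0.3 × 0.7 = 0.42. P(enter) = 0.49 + 0.42 × 0.343 = 0.634.
- DLT risk half the true rate (0.15): no DLT in three, 0.49 × 0.85 = 0.4165; exactly one, 0.42 × 0.85 + 0.49 × 0.15 = 0.4305. P(enter) = 0.4165 + 0.4305 × 0.343 = 0.564.

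The comparison value with three fully treated patients is 0.494. The two risks in the partly treated patient are assumptions.

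**The case against.** The strongest reply is that the two paragraphs differ by timing: removal applies during the SBRT weeks, and continued evaluability applies afterwards, over the 6-month window. That is a natural reading, but the text does not state it, and it would still clash with section 6.3.1.1, under which a patient is evaluable from first treatment.

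A second reply is that no section orders a DLT to be discarded, and that sections 6.3.1.1, 11.4 and 6.3.2.3.2 lean towards keeping it. This is right. A reader might infer that the plan drops DLTs from the 3+3 count; the documents support only that it leaves the matter open.

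A third reply concerns direction. A reader might infer that removal is tied to toxicity, and so that unsafe levels pass more often than the table shows. The stated trigger is a need for anti-cancer treatment, not toxicity, and it covers only the two treatment weeks, with immunotherapy exempt. Some listed DLTs, such as dyspnea or pericardial effusion, could accompany deterioration that prompts such treatment, but nothing in the documents shows a link. The upward figures in step 3 arise when DLT patients are removed more often than others. This objection stands in full against any claim of a known bias. It does not touch the conflict between the two rules or the one-patient results in step 2.

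**Conclusion.** The point holds as a conflict between rules together with a missing counting rule. Section 7 assigns opposite outcomes to a Phase I patient given systemic treatment other than immunotherapy during the SBRT weeks, and section 11.1 does not say whether that patient's DLT counts.

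The effect can be decisive in a single case: at a true DLT rate of 30%, 0.343 against 0.803 when the patient has the only DLT in the first three, and 0 against 0.240 when the patient has one of two. These results assume independent outcomes and a fully treated replacement at the same dose level.

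The average effect is not determinable. At the same rate, 0.494 becomes 0.54 to 0.61 if 10 to 25% of DLT patients and no others are removed; it is unchanged if removal is unrelated to DLT; it falls, for example to 0.420, if mainly DLT-free patients are removed. The documents therefore do not support saying that the table in 11.1 is wrong or that the plan is biased towards passing unsafe levels.

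**What to change.** Reconcile section 7 with section 6.3.1.1, and carry the result into section 11.1:

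- Any patient who has started SBRT continues DLT follow-up for the full 6-month window, whether or not replaced.
- Any DLT observed in such a patient counts in the 3+3 decision for that dose level.
- Replacement otherwise concerns response evaluability. Section 7's existing rule that non-protocol treatment for worsening of index lesions is scored as progression stays in force, so that replacement does not erase a response failure.
- State separately whether a DLT-free patient who did not complete the planned fractions fills a Phase I slot or is replaced. This needs an explicit choice, because step 5 shows that filling the slot can raise Phase II entry.
- Report the number of removals and the reasons, by cohort and dose level.

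The cost is mainly wording, since sections 6.3.1.1 and 11.4 already provide for toxicity assessment of treated patients. The downside is that a DLT partly due to the other systemic therapy may be counted against SBRT. Section 6.2 limits this in part, because its grade 3 category requires the toxicity to be a direct result of therapy. No change is proposed to when systemic therapy is given.

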8. TISSUE/SPECIMEN SUBMISSION

Not applicable.

9. PARTICIPANT ASSESSMENTS

Evaluation of response. All participants included in the study will be assessed for response to treatment, unless the subject received systemic therapy prior to the 6 week assessment.. Response in this study will be defined as disease control in the treated lesion at 6 weeks. We will continue to assess response and consider best overall response as a secondary objective.

Each participant will be assigned one of the following categories: 1) complete response, 2) partial response, 3) stable disease, 4) progressive disease, 5) early death from malignant disease, 6) early death from toxicity, 7) early death because of other cause, or 9) unknown (not assessable, insufficient data). By arbitrary convention, category 9 usually designates the "unknown" status of any type of data in a clinical database.

Disease control at 6 weeks will include complete response (CR), partial response (PR) and stable disease (SD).

Patients will be seen weekly during treatment for physical examination and assessment of acute side effects. They will then be seen at one month from the end of study treatment for physical examination, A CT at will be done at 6 weeks post completion of SBRT and then every three months with physical examination and CT scan of the chest during the first year, followed by every 6 months for the next year and then annually until year 5, as is considered standard of care. (See: Study Calendar)

The lesion or lesions treated will be measured as well as new lesions identified. Pulmonary function tests will be done at 3 months post treatment, then at 9 months.

9.1 Response Criteria

9.1.1 Evaluation of Target Lesions (response will be measured using CT scans)

Complete Response (CR)

Disappearance of all target lesions. Any pathological lymph nodes (whether target or non-target) must have reduction in short axis to ≤ 10 mm.

Partial Response (PR)

At least a 30% decrease in the sum of the diameters of target lesions, taking as reference the baseline sum diameters

Progressive Disease (PD)

At least a 20% increase in the sum of the diameters of target lesions, taking as

reference the smallest sum on study (this includes the baseline sum if that is the smallest on study). In addition to the relative increase of 20%, the sum must also demonstrate an absolute increase of at least 5 mm.

NOTE: The appearance of one or more new lesions will not be considered progression.

Stable Disease (SD)

Neither sufficient shrinkage to qualify for PR nor sufficient increase to qualify for PD, taking as reference the smallest sum diameters while on study. (Note: a change of 20% or more that does not increase the sum of the diameters by 5 mm or more is coded as stable disease). To be assigned a status of stable disease, measurements must have met the stable disease criteria at least once after study entry at a minimum interval of 6 weeks.

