3. PARTICIPANT SELECTION

3.1 Eligibility Criteria

- 1. Diagnosis of Ewing sarcoma, rhabdomyosarcoma, osteosarcoma, non-rhabdomyosarcoma soft tissue sarcoma, Wilms tumor or other primary renal tumor (including clear cell and rhabdoid)
- 2. Age ≤21 years
- 3. Must be capable of treatment without general anesthesia
- 4. Lesion size 4 mm 3 cm

5. Subjects who have lesions within 2 cm of central structures*, will be eligible on a case-by-case basis

*Tumor within or touching the zone of the proximal bronchial tree, defined as a volume 2 cm in all directions around the proximal bronchial tree (carina, right and left main bronchi, right and left upper lobe bronchi, intermedius bronchus, right middle lobe bronchus, lingular bronchus, right and left lower lobe bronchi).

- 6. Pulmonary metastases found at relapse (does not have to be first relapse); no more than 3 lesions per hemi-thorax will be treated but other lesions in the lung may be present
- 7. Greater than 5 weeks from doxorubicin at the time of consent, with radiation to be initiated no less than 6 weeks from doxorubicin
- 8. Informed consent/assent
- 9. Life expectancy > 3 months
- 10. Pulmonary function FEV₁ ≥ 50% of predicted
- 11. Concurrent immunotherapy is allowed

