3.2 Exclusion Criteria

- 1. Prior whole-lung or hemi-thorax irradiation of greater than 12 Gy received less than 6 months prior to consent (focal radiotherapy to the thorax is not an exclusion)
- 2. Lesion larger than 3 cm in diameter
- 3. Patients for whom surgery would be deemed appropriate rather than radiotherapy.

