6. RADIATION THERAPY

6.1 Dose Specifications: 3D Conformal Radiotherapy (3DCRT) or IMRT

- 6.1.1 Treatment simulation: The patient will undergo simulation (treatment planning) in a standard stereotactic immobilization device. The simulation will be done using 4DCT to account for respiratory motion. A free-breathing CT scan will also be performed using 2.5-mm slices. Abdominal compression will be used if the tumor moves more than 1 cm with respiratory motion. This approach is the standard protocol for SBRT at our institution.
- 6.1.2 Contours: The tumor nodule or nodules will be contoured
 - 6.1.2.1 Internal tumor volume (ITV): gross tumor plus margin for internal motion.
 - 6.1.2.2 Planning target volume (PTV): will be ITV plus 5 mm

6.1.2.3 Organs at risk will be defined by the physician and/or the treatment planner:

- Total lung: total lung volume-ITV
- Heart: Defined from apex to first slice of great vessels
- Spinal cord
- Chest wall
- Skin
- Ribs abutting tumor
- Esophagus: defined 5 cm above and below PTV
- Proximal bronchial tree: defined from inferior 2 cm of trachea to lobar bronchi, to point of bifurcation into segments
- Brachial plexus

6.1.2.4 Dose Level 1 will be the starting dose for patients with Wilms/Renal tumor. Dose Level 2 will be the starting dose for patients with Ewing sarcoma/Rhabdomyosarcoma (non-renal). SEE APPENDIX: A.

Treatment will be delivered over 1-2 weeks. Delivery of hypofractionated radiotherapy (i.e., using a small number of fractions) makes it challenging to determine normal-tissue dose constraints. However, we will use very conservative critical-structure dose limits based on those used in published experience in SBRT in adults. See Appendix B for UTSW Dose Constraints.

6.1.2.5 Dose Levels for each target lesion are as follows:

Dose level 1 - 8 Gy x 3 Dose level 2 - 10 Gy x 3 Dose level 3 - 12 Gy x 3

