9.1.2 Evaluation of New Lesions

The appearance of new lesions will not be considered Progressive Disease (PD). The goal of this study is to evaluate the safety and efficacy of stereotactic radiotherapy to individual lesions. If subject develops new lesions, this would not impact the study results. For example, a new lesion might be amenable to SBRT. However, on this protocol such new lesions will not be treated.

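### Disease control is scored on the summed diameters of all treated lesions, so in patients with two or more treated lesions one irradiated lesion can progress while the patient counts as controlled

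*Combined protocol and SAP*

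**What the plan says.** The combined protocol and SAP describes the unit of the Phase II primary endpoint in several ways.

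- Section 2.2.2 sets the objective as response six weeks after SBRT, defined by RECIST.
- Section 9: "Response in this study will be defined as disease control in the treated lesion at 6 weeks". Each participant receives one category, and CR, PR and SD all count as control.
- Section 9.1.1 defines PR and PD on the sum of target-lesion diameters. PD is "At least a 20% increase in the sum of the diameters of target lesions", and the sum must also rise by at least 5 mm. SD is whatever falls between PR and PD.
- Section 9.1.2 explains why new lesions are not progression: "The goal of this study is to evaluate the safety and efficacy of stereotactic radiotherapy to individual lesions".
- Section 11.3 places the endpoint in the treatment field.

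On the number of lesions, Section 3.1 says "no more than 3 lesions per hemi-thorax will be treated but other lesions in the lung may be present". Section 6.1 (item 6.1.2.5) sets the dose per target lesion, so I take the target lesions to be the irradiated ones. The only route to progression outside the sum is in Section 7: non-protocol surgery or chemotherapy given because the index lesions have worsened.

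**The concern.** SBRT is a local treatment, and the plan uses that fact to justify ignoring new lesions. The same reasoning sits badly with a rule that lets shrinkage or stability in one irradiated lesion offset growth in another. Section 9.1.1 gives no lesion-level progression rule, does not cap the number of lesions in the sum, and does not say how a patient with mixed outcomes is scored.

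The category feeds a decision. Under Section 11.1, five responders among fifteen patients end escalation in that cohort, and the dose level is taken to be tolerable and effective. If some of the five carry a progressing treated lesion, the dose is declared effective partly on local failures.

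**Working it through.** **The plan's own design figures.** Inputs from Section 11.1: 7 patients in stage 1, continue with at least 2 responses, 15 in total, success with at least 5. The success probability at true rate p is the sum over x = 2 to 7 of C(7,x) p^x (1−p)^(7−x) × P[Bin(8,p) ≥ 5−x].

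- p = 0.20: success 0.141, early stop 0.577 (plan: 0.14 and 0.58).
- p = 0.50: success 0.903, early stop 0.0625 (plan: 90% and 0.06).

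The figures reproduce. They do not depend on how a patient is scored; the scoring decides which patients are counted.

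**Number of lesions.** 2 × 3 = 6 treated lesions at most. This is derived from Section 3.1; the plan does not state it as a count of target lesions.

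**Reference.** The six-week CT is the first scheduled after treatment, so the reference sum at that point is baseline.

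**Growth needed for PD.** Take k equal lesions of diameter d, with all but one unchanged. The sum reaches PD when that one lesion grows by max(0.2·k·d, 5 mm). Judged alone, it reaches PD at max(0.2·d, 5 mm).

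| d | k = 1 | k = 2 | k = 3 | k = 6 |
|---|---|---|---|---|
| 10 mm | 5 mm (50%) | 5 mm (50%) | 6 mm (60%) | 12 mm (120%) |
| 20 mm | 5 mm (25%) | 8 mm (40%) | 12 mm (60%) | 24 mm (120%) |
| 30 mm | 6 mm (20%) | 12 mm (40%) | 18 mm (60%) | 36 mm (120%) |

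The k = 1 column is the fair comparator. With the others unchanged there is no dilution while 20% of the baseline sum is at most 5 mm, that is, while the sum is at most 5/0.2 = 25 mm. For two equal lesions this means 12.5 mm or less each; for three, about 8.3 mm or less.

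If the other lesions each shrink by 30%, the growing lesion must increase by 0.2k + 0.3(k−1): 70% for k = 2, 120% for k = 3 and 270% for k = 6, subject to the 5 mm minimum.

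**Worked patients.**

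| Baseline (mm) | Six weeks (mm) | Sum | By the sum | Growing lesion(s) alone |
|---|---|---|---|---|
| 10, 20 | 15, 20 | 30 to 35 (+16.7%) | SD | +50%, +5 mm: PD |
| six of 10 | 20, five of 10 | 60 to 70 (+16.7%) | SD | +100%, +10 mm: PD |
| 10, 10 | 15, 5 | 20 to 20 (0%) | SD | +50%, +5 mm: PD |
| 10, 10, 10 | 16, 2, 2 | 30 to 20 (−33%) | PR | +60%, +6 mm: PD |
| 10, 10 | 14, 14 | 20 to 28 (+40%, +8 mm) | PD | +4 mm each: not PD |

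The first four patients count as controlled despite a progressing treated lesion. The last shows the reverse: the sum detects joint growth that a lesion-by-lesion rule would miss.

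**Possible consequence, under an assumed shift.** If masking raised the observed control rate from 20% to 30%, the chance of passing would go from 0.141 to 0.432. The size of that shift is an assumption; the documents do not allow it to be estimated.

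**The case against.** The strongest defence is that Section 2.2.2 names RECIST and that Section 9.1.1 writes those criteria as a sum. Section 9 gives each participant one category and also refers to one or more treated lesions, so its singular can be read generically. The sentence in Section 9.1.2 explains why new lesions are ignored; it does not promise a per-lesion endpoint. This stands to the extent that a reader should not infer that the plan measures something wholly different from its endpoint. It does not settle mixed outcomes, and the plan has already left RECIST for new lesions on local-effect grounds.

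Section 7 is a partial safeguard, and the worst failures are where it is most likely to apply. It does not cover growth seen on the six-week CT that leads to no surgery or chemotherapy.

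A reader might also infer that all the bias runs towards control, so that a pure per-lesion rule would be the stricter one. The documents do not support this. Because the 5 mm minimum applies to the sum, two 10 mm lesions both reaching 14 mm are PD by the sum and not PD singly. Replacing the sum rule would turn such patients into controls.

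Finally, the large dilution figures need many, larger or unequal lesions, or clear shrinkage of the others.

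**Conclusion.** The point holds for patients with two or more treated lesions. As written, the rule can count a patient as controlled when an irradiated lesion meets the protocol's own progression thresholds, and two lesions are enough for this. The effect is zero for single-lesion patients, and zero with the other lesions unchanged when the baseline sum is 25 mm or less. For six equal 20 mm lesions with the others unchanged, the growth required of one lesion rises from 25% to 120%.

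A reader might go on to infer that the 5-of-15 count is inflated by a material amount. The documents give no distribution of lesions per patient, so the number of misclassified patients is unknown and may be zero. The conclusion rests on the target lesions being the irradiated lesions and on the 20% and 5 mm thresholds being the intended mark of failure for a single lesion. The two-stage design itself is sound as stated.

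**What to change.** 1. Reconcile Sections 2.2.2, 9, 9.1.1, 9.1.2 and 11.3 so that they name one unit and one scoring rule for the primary endpoint.
2. Keep the patient as the unit of the two-stage test and keep the sum rule. Count disease control at six weeks only if neither the sum nor any single treated lesion shows an increase of at least 20% and at least 5 mm over its own reference. This deals with the masked single failure without losing joint growth that only the sum detects.
3. Report as supportive the sum-only RECIST category and a lesion-level control table, with an interval that allows for clustering of lesions within patients. Tabulate the number of treated lesions per patient, so that the reach of the issue can be seen.
4. Confirm that the 20% and 50% rates in Section 11.1 still suit the clarified endpoint.

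The cost is wording and a little programming, since Section 9 already has the treated lesions measured. Stage sizes and thresholds stay the same. The added condition can only leave the observed control rate unchanged or lower it, probably slightly, and it puts more weight on measurement error in single lesions.
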